We anticipate that empagliflozin will increase norepinephrine spill over to the plasma in T2DM patients as well, and that the increase in norepinephrine spillover will strongly correlate with the increase in HGP. Because the methodology utilized in the present study measures the rate of total body norepinephrine spill over, it is possible that the increase in epinephrine spill over from specific organs, e.g. kidney and splanchnic (primarily hepatic) tissue, will be diluted in the systemic circulation. Thus, it is possible that only a modest effect of empagliflozin on sympathetic activity will be detected. In such a scenario, measurement of organ specific (58), e.g. renal norepinephrine spill over (with renal vein catheterization) and splanchnic (with intraduodenal ³H-NE infusion and arterial or hepatic vein sampling) can be employed to quantitate the change in sympathetic activity in the kidney and liver.

Sample Size Calculation We powered the study to detect a significant increase in the basal rate of HGP following empagliflozin administration versus placebo. In previous studies, the increase in the rate of HGP versus placebo following empagliflozin administration was 0.34 ± 0.26 mg/kg.min. Therefore, we computed that 30 subjects in 2:1 randomization (20 empagliflozin and n=10 placebo) provide >90% power to detect a significant difference in HGP between empagliflozin-treated and placebo-treated subjects (in 3 groups comparison) at alpha <0.05. Therefore, to ensure 30 completers, we have set the sample size at 36 in each group.

Item 7 Risks Section:

Complete the following table to describe the risks of all **research procedures** listed in Step 2, Institutional Form (items 28-34). *Do not list risks of Routine care procedures here.*

X N/A, Risks are described in the informed consent document – do not complete this table.

Research procedures	Risks
example: 
• History and physical• Questionnaire• Laboratory tests	List the reasonably expected risks under the following categories as appropriate:
Add or delete rows as needed	
	

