Our recent findings about the effect of empagliflozin on glucose metabolism in NGT and IFG subjects (Figures 10-14) and the effect of SGLT2 inhibitors on pyruvate oxidation in hepatocytes *in vitro* (Figure 15) require an update of our previous scheme (13) (Figure 6) describing the mechanism(s) responsible for the metabolic actions of SGLT2 inhibitors in T2DM patients. We suggest the following working hypothesis (Figure 16) which we will be testing in the current grant request: (1) Because empagliflozin did not stimulate glucagon secretion or inhibit insulin secretion in NGT subjects, it is likely that glucosuria stimulates HGP, at least initially, via mechanisms other than the increase in plasma glucagon concentration and decrease in plasma insulin concentration. Of note, the increase in HGP begins rapidly following dapagliflozin administration and before there is a significant increase in plasma glucagon concentration (Figure 2). This suggests a neurogenic origin, which results from activation of the renal nerves which communicate directly with the liver via neural connections in the portal circulation or indirectly via connections to the CNS. Consistent with this hypothesis, a recent study has demonstrated that the increase in HGP in dogs following hypoglycemia is markedly influenced by the brain (43). Further, renal denervation in experimental animals caused a significant increase in hepatic norepinephrine content (44). In the present grant proposal, we will measure the effect of empagliflozin on sympathetic activity with ³H-NE infusion; (2) In addition to inhibition of renal glucose absorption, SGLT2 inhibitors likely exert a direct inhibitory action on mitochondrial metabolism (possibly by inhibiting complex I[42]) causing inhibition of pyruvate oxidation and reduction in glucose oxidation. (3) The inhibition of glucose oxidation results in a reciprocal increase in fat oxidation and acetyl Co-A levels (4) The increase in fat oxidation aims to provide an alternative energy source to meet the metabolic demands of the cell. Because fat oxidation is associated with generation of FADH which can generate ATP via donating electrons to complex 2, thereby, bypassing the block at complex 1. (5) the decrease in the fasting plasma glucose concentration in T2DM patients following glucosuria stimulates glucagon secretion and inhibits insulin secretion resulting in an increase in plasma glucagon to insulin ratio; (6) the increase in glucagon to insulin ratio further stimulates and maintains the increase in HGP and stimulates the conversion of acetyl Co-A to ketones (possibly by stimulating the expression of hydroxyl methylglutaryl Co-A synthase [HMGS], the rate limiting step for the conversion of acetyl Co-A to beta hydroxybuterate [45,46]); (7) in subjects with NGT, SGLT2 inhibition does not affect the FPG concentration. Thus, plasma glucagon and insulin concentrations are not affected by SGLT2 inhibition, and the plasma ketone concentration does not increase (Figure 14). In the present grant request, we will test these hypotheses by: (1) examining the effect of empagliflozin on HGP, substrate oxidation, plasma ketone/lactate/insulin/glucagon concentrations, hepatic fat content, basal hepatic glucose uptake and sympathetic nervous system activity in NGT, IFG and T2DM patients with FPG concentration <160 mg/dl using state-of-the-art techniques. Because empagliflozin does not affect the FPG, insulin and glucagon concentrations in NGT subjects, this allows us to provide definitive evidence for the role of sympathetic activation in the increase in HGP caused by empagliflozin, and (2) examination of the effect of empagliflozin on substrate oxidation, hepatic fat content, FPG concentration, and hepatic glucose uptake during the fasting state in IFG

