
IFG individuals, we hypothesize that: (1) the change in plasma insulin and glucagon concentrations in T2DM individuals is likely the effect of the decrease in plasma glucose concentration; (2) signals other than the change in glucagon to insulin ratio (likely neuronal) are activated by glucosuria and stimulate HGP in NGT and IFG individuals; (3) SGLT2i cause an increase in basal hepatic glucose uptake in IFG subjects and lead to a decrease in FPG; and (4) to examine these hypotheses, we suggest the following specific Aims:

Specific Aim 1: We will measure FPG, bHGP (³H-glucose infusion), whole body fat oxidation (indirect calorimetry), plasma insulin, glucagon, FFA, ketone and lactate concentrations, and hepatic fat content (¹H-MRS) in IFG, NGT and T2DM patients (drug naïve with FPG <160 mg/dl) at baseline and at day 1 and 4 weeks after treatment with SGLT2i (empagliflozin)

Specific Aim 2: Measure autonomic balance (with heart rate variability) and sympathetic nervous system activity (³H-norepinephrine turnover) in IFG, NGT and T2DM subjects (drug naïve with FPG <160 mg/dl) at baseline and at day 1 and 4 weeks of treatment with SGLT2i (empagliflozin).

SIGNIFICANCE

The present study will add new insight about the mechanism(s) underlying the multiple metabolic actions of SGLT2 inhibitors in T2DM patients (1). Our preliminary results demonstrate that, this class of drugs, in addition to the inhibition of renal glucose transport, exerts a direct effect on glucose oxidation. We and others previously have shown that SGLT2 inhibitors exert multiple metabolic actions on glucose and fat metabolism with significant clinical implication in T2DM patients: (1) stimulate the basal rate of HGP which offset approximately 50% of urinary glucose loss produced by the drug and ameliorate the drug efficacy in lowering the plasma glucose concentration; (2) increase fat oxidation and ketone production, thus, increasing the susceptibility to diabetic ketoacidosis; and (3) increase plasma glucagon concentration which could contribute to the increase in HGP and ketone production. The results of the present study will define the mechanisms responsible for these actions of SGLT2 inhibitors and pave the rode for the development of therapeutic strategies to mitigate their adverse events, e.g. risk of ketoacidosis, and increase the efficacy of this class of drugs to lower the plasma glucose concentration in T2DM patients.

Item 5

Study Population(s) Being Recruited

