In your recruitment plan, how many different populations of prospective subjects do you plan to target? Provide number: 2

Identify the criteria for **inclusion**:

Identify the criteria for **exclusion**:

e.g., a population can be individuals with type 2 diabetes controlled with diet and/or a population of healthy controls. Or a population can be individuals attending an education program, etc.
 
List each different population on a separate row and provide a short descriptive label: (e.g., normal-healthy, diabetics, parents, children, etc.)
 
To add rows use copy & paste
		
Type 2 diabetic subjects	1) FPG< 240 mg/dl 2) Age 18-70 years 3) eGFR>60 ml/min 4) weight stable ($\pm 4\text{Lb}$) in the preceding 3 months 5) Good general health	1) Use of an insulin or SGLT2 inhibitor medications affects glucose tolerance 2) Major organ disease 3) eGFR <60 ml/min 4) type 1 diabetes
Subjects with FPG<126 mg/dl	1) FPG<126 and 2-h PG <200 mg/dl 2) Age 18-70 years 3) eGFR>60 ml/min 4) weight stable ($\pm 4\text{Lb}$) in the preceding 3 months 5) Good general health	1) Use of medications that affect glucose tolerance 2) Major organ disease 3) eGFR <60 ml/min
Sub-Study: Type 2 diabetic	1) current diagnosis of Type 2 Diabetes 2) fasting plasma glucose concentration <300 mg/dl 3) Subjects must be drug naïve or on stable dose of metformin and/or sulfonylurea in the preceding 3 months 4) body weight has been stable (± 3 lbs) over the preceding three months 5) does not participate in an excessively heavy exercise 6) good general health as determined by physical exam, medical history, blood chemistries, CBC, TSH, urinalysis, and EKG	1) eGFR > 60 ml/min 2) hematocrit > 34%, 3) allergy to iodine 4) Major organ disease
Sub-Study: non-diabetic	1) No diagnosis of diabetes (FPG <126 mg/dl) 2) body weight has been stable (± 3 lbs) over the preceding three months 3) does not participate in an excessively heavy exercise 4) good general health as determined by physical exam, medical history, blood chemistries, CBC, TSH, urinalysis, and EKG	1) eGFR > 60 ml/min 2) hematocrit > 34%, 3) allergy to iodine 4) Major organ disease

Item 6

Research Plan / Description of the Research Methods *a. Provide a comprehensive narrative describing the research methods. Provide the plan for data analysis (include as applicable the sample size calculation).*

Step-by-Step Methods: Study Design:

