Follow Up Visits: at weeks 1, 2, 4, 6, 8 and 10 after the start of treatments, subjects will come to the CRC for follow-up visits. At week 4 and 8 visits, medical history and physical exam will be performed. Body weight, blood pressure and pulse will be measured. Blood sample will be drawn for the measurement of fasting plasma glucose, insulin, glucagon, FFA, HbA1c, Pro BNP and ketones. Blood will also be drawn to monitor renal function with ketones, electrolytes, glucosuria, and monitor and mitigate urinary tract infections.

If the treatment period is extended, patients will continue to be followed up every 2-4 weeks and provided with the study medications until the repeat tests are completed. If the circumstances prohibit clinic visits for follow-up, the study team will perform a phone follow-up visit to ensure patient adherence, information collection, and adverse events monitoring.

Sub-Study 1:

36 T2DM patients will participate in this study, The T2DM subjects enrolled in the main study will also be subjects enrolled into the sub-study. Each subject will receive a measurements of hepatic glucose production with stable isotope (6,6,-D2-glucose) plus indirect calorimetry with empagliflozin (n=24) or placebo (n=12) administration. Norepinephrine turnover measurement will be performed at baseline (before the empagliflozin or placebo administration) and 5 hours after the drug administration. On a separate day subjects will return to the CRC and the measurement of hepatic glucose production and NE turnover studies will be repeated with a glucose clamp.

Specific Methods:

Measurement of Hepatic Glucose Production With 6,6,D2-glucose, ³H-NE infusion and Drug Administration:

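### Aims 1 and 2 describe drug-naive T2DM patients with FPG below 160 mg/dl, but the main-study eligibility criteria admit FPG below 240 mg/dl and set no drug-naive requirement

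*Combined protocol and SAP*

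**What the plan says.** **The population in the Aims.** Item 4, Specific Aims 1 and 2, both limit T2DM patients to those who are "drug naïve with FPG <160 mg/dl". The working hypothesis at the end of Item 3 gives the same glucose limit, naming "NGT, IFG and T2DM patients with FPG concentration <160 mg/dl".

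**The population in the criteria.** The main-study T2DM row of Item 5 begins "1) FPG< 240 mg/dl 2) Age 18-70 years". None of its inclusion criteria requires drug-naive patients. Its drug exclusion reads "Use of an insulin or SGLT2 inhibitor medications affects glucose tolerance", which is not a complete sentence and names only two drug classes.

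**The sub-studies.** Sub-study 1 (Item 6) gives no FPG limit and takes its patients from the main study: "The T2DM subjects enrolled in the main study will also be subjects enrolled into the sub-study". Item 5 also has a T2DM row headed only as a sub-study, with "fasting plasma glucose concentration <300 mg/dl" and "Subjects must be drug naïve or on stable dose of metformin and/or sulfonylurea in the preceding 3 months".

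**The analysis.** The Data Analysis Plan in Item 6 compares empagliflozin with placebo within each of NGT, IFG and T2DM, using ANOVA with Bonferroni post hoc tests. It relates the HGP change to the change in norepinephrine spillover by Pearson correlation within each treatment group. It names no covariates.

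**The concern.** A patient with FPG between 160 and 239 mg/dl, or one taking another glucose-lowering drug, appears eligible under Item 5 but lies outside the population of both Aims. Nothing in the documents explains the wider limit or the absence of the drug-naive condition.

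The protocol's own reasoning puts baseline FPG close to the mechanism under test:

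- The first hypothesis in Item 4 holds that insulin and glucagon changes in T2DM follow from the fall in plasma glucose.
- The Background reports glucosuria of 45, 50 and 97 g/day in NGT, IFG and T2DM subjects on empagliflozin.
- It also reports that the fall in FPG among IFG subjects was related to FPG (r = -0.61).

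Background therapy matters for the comparison across groups. The non-diabetic row of Item 5 excludes drugs that affect glucose tolerance, whereas the T2DM row names only insulin and SGLT2 inhibitors. If treated patients enter, a T2DM versus NGT or IFG comparison mixes disease with therapy. Sub-study 2 withholds metformin and sulfonylurea on study days; the main-study methods do not mention background therapy.

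**Working it through.** **1. The definitions side by side**

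| Place | FPG limit (mg/dl) | Background therapy |
|---|---|---|
| Item 3, working hypothesis | <160 | not stated |
| Item 4, Aims 1 and 2 | <160 | drug naive |
| Item 5, main-study T2DM row | <240 | no drug-naive rule; insulin and SGLT2 inhibitors named as exclusions |
| Item 6, Sub-study 1 | none of its own | none of its own; uses main-study patients |
| Item 5, Sub-Study T2DM row | <300 | drug naive, or stable metformin and/or sulfonylurea |
| Item 6, Sub-study 2 | <300 | same as the row above |

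The first three rows concern the same patients and disagree. The ratio of ceilings is 240/160 = 1.5. The limits are nested: anyone below 160 is also below 240, but not the reverse.

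**2. The plan's own power figure**

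Inputs from the Item 6 sample size section: difference 0.34, SD 0.26 mg/kg.min, 20 versus 10 completers, alpha 0.05 (taken as two-sided).

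- SE = 0.26 × √(1/20 + 1/10) = 0.26 × 0.387 = 0.1007
- 0.34/0.1007 = 3.38, and 3.38 - 1.96 = 1.42, giving power of 92.2% (normal approximation) or 90.3% (noncentral t)
- Enrolment: 30/(1 - 1/6) = 36

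The stated figure of more than 90% and the 36 per group both reproduce. Reconciling the definition does not alter them.

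**3. What a wider group could do to precision (illustration)**

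The documents give no SD of HGP by FPG range. Holding the difference at 0.34 and assuming a larger SD, power by the normal approximation is:

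| Assumed SD | Power, 20 vs 10 |
|---|---|
| 0.26 (plan) | 92.2% |
| 0.30 | 83.3% |
| 0.35 | 70.8% |
| 0.40 | 59.3% |

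**4. What adjustment costs and gains**

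With 30 completers, one covariate takes the residual degrees of freedom from 28 to 27, or to 26 if therapy is added. For one roughly normal covariate, chance imbalance inflates the variance of the treatment estimate on average by 1 + 1/(30 - 4) = 1.038, while adjustment multiplies it by 1 - ρ². Break-even is at ρ² = 1 - 26/27 = 0.037, or |ρ| of about 0.19. The value of ρ for HGP change is not given. At an assumed 0.3 the factor is 0.91 × 1.038 = 0.94; at 0.5 it is 0.75 × 1.038 = 0.78.

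Chance imbalance is not negligible without adjustment: the arm difference in mean FPG has a standard deviation of √(1/20 + 1/10) = 0.39 of the between-patient SD.

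**5. The correlation**

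Suppose HGP change and norepinephrine change each correlate with baseline FPG at r and have no link once FPG is fixed. Their raw Pearson correlation is then r². Assumed r of 0.5, 0.6 and 0.7 gives 0.25, 0.36 and 0.49. Randomisation does not remove this, because the correlation is computed within a treatment arm.

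**The case against.** **Item 5 governs.** It is the form's place for eligibility, whereas Item 4 states purpose. The Aims look like text carried over from a grant: they still refer to 4 weeks of treatment, while Item 6 explains an extension to 12. This is plausible, and it makes confusion at screening less likely. But no passage says that Item 5 supersedes the Aims, and the explanation in Item 6 covers treatment duration only. If Item 5 does govern, Items 3 and 4 need correcting.

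**Randomisation protects the main contrast.** This stands. Patients are randomised 2:1 within each group, the drug effect is estimated within each group, and the sample size addresses that comparison. Neither baseline FPG nor background therapy biases it systematically. Randomisation does not protect comparisons across glucose-tolerance groups or the within-arm correlation.

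**A ratio of ceilings is not an effect.** This also stands. The factor of 1.5 describes what is permitted, not the mean FPG of those enrolled.

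**A stronger reading is tempting.** A reader might infer a third T2DM definition from the FPG <300 row, and two ceilings on the Sub-study 1 patients. The documents do not support this. The row matches the Sub-study 2 subject description on FPG, therapy and weight stability. It lists the same eGFR, hematocrit and iodine-allergy items, although the direction of the first two is reversed in the table. Iodine allergy is relevant to indocyanine green, which only Sub-study 2 uses. The row is paired with a non-diabetic row, and only Sub-study 2 has a non-diabetic sub-study group (18 subjects). A separate sub-study may set its own limit. What remains is that the row carries no number.

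**Conclusion.** The point holds for the main study. The Aims and the eligibility criteria describe different T2DM populations, and the enrollable one is wider: its FPG ceiling is 1.5 times as high, and drug-naive status is not required. Sub-study 1 inherits this discrepancy.

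The definitions are inconsistent rather than mutually exclusive, since the FPG limits are nested. Item 5 does not require background therapy; it leaves unclear which drugs are permitted. The ratio 300/160 = 1.88 should not be used, because the 300 mg/dl limit belongs to Sub-study 2.

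The consequence is for interpretation, and possibly for precision, not for the validity of the randomised contrast. The power losses in the working depend on assumed SDs and are illustrations. The case for adjusting rests on FPG being related to the response. The protocol supports that only indirectly: r = -0.61 is for the fall in FPG rather than HGP, and comes from a group of 8 IFG subjects, so it is imprecise. The correction should be made, but no stated sample size or power figure is affected.

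**What to change.** 1. Reconcile the Item 3 working hypothesis, Aims 1 and 2 in Item 4, and the main-study T2DM row of Item 5 to one definition, covering both the FPG ceiling and permitted background therapy. Rewrite the garbled drug exclusion as a complete sentence. No view is taken here on which limit or therapy rule is right.
2. Label the two Sub-Study rows in Item 5 as Sub-study 2, and state that Sub-study 1 uses the main-study criteria.
3. In the T2DM analyses of HGP and norepinephrine spillover, replace the unadjusted ANOVA with a model containing treatment and baseline FPG as a continuous covariate.
4. Relate HGP change to norepinephrine change by a partial correlation given baseline FPG, within each treatment arm.
5. Add background therapy (none versus any) to these analyses only if treated patients are admitted. If all are drug naive it is constant and cannot be estimated.

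Cost: wording in Items 3 to 6, and one or two degrees of freedom with about 20 versus 10 completers. No new measurement is needed: fasting plasma glucose is taken at the baseline HGP test, and background therapy can be taken from the screening medical history.

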After screening, subjects will receive the following tests: (1) Measurement of hepatic glucose production, substrate oxidation and plasma ketone/lactate/insulin/glucagon concentrations; (2) (Measurement of whole body norepinephrine turnover with ^3H -norepinephrine infusion; (3) Measurement of heart rate variability; (4) Measurement of liver fat content with ^1H -MRS; (5) 75-grams oral glucose tolerance test (OGTT)

The studies will be performed in a random order.

After the completion of the above studies, subjects in each group will be randomized (in 2:1 ratio) to receive for 12 weeks, empagliflozin 25 mg per day (n=24) or placebo (n=12), in a double blind fashion. The drug treatment will be started (day 1) on the day of the second hepatic glucose measurement (see specific details below). On day 2, the measurement of heart rate variability and norepinephrine turnover will be repeated. Subjects will continue treatment with the drug (empagliflozin or placebo) that they received during the second hepatic glucose measurement for 12 weeks and at the end of 12 weeks, all baseline tests will be repeated.

The treatment period could be extended based upon the circumstances until the repeat studies are completed.

Tests	Baseline	Day 1-3	12 Weeks
OGTT	OGTT		OGTT
HGP	Short	Long	Short
NE	NE	NE	NE
MRI	MRI		MRI
DEXA	DEXA		
HRV	HRV	HRV	HRV

The metabolic effects of empagliflozin lasted for 2 weeks in our previous studies (7). However, Ferrannini and colleagues (40) reported that at 4 weeks, the glucose effects of empagliflozin (HGP) are attenuated while the fat effects (fat oxidation and ketone production) are enhanced. Therefore, to evaluate the long term metabolic impact of SGLT2 inhibition, we decided to extend the treatment period in the current study to 12 weeks.

Specific Methods:

Screening: Medical history and physical examination will be performed. Blood samples will be drawn for CBC, blood chemistries, lipid profile, thyroid function and HbA1c. EKG will be performed.

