Measurement of Hepatic Glucose Production with ^3H -glucose infusion (HGP – short): The rate of endogenous (primarily reflecting liver) glucose production will be measured with ^3H -glucose infusion as previously described (7). After a 10 hour overnight fast, a prime (25 $\mu\text{CiXFPG}/100$) - continuous (0.25 μCi) infusion of ^3H -glucose will be started and continued for 3 (4 in T2DM patients) hours. After 2 hours (3 hours in T2DM patients) of tracer equilibration, blood samples will be drawn from the catheter on the dorsum of the hand at 120, 130, 140, 150, 160, 170 and 180 minutes (from 180-240 minutes in T2DM patients). Plasma glucose, insulin, glucagon, GLP-1, cortisol, growth

hormone, ketones, lactate, bicarbonate and catecholamine concentrations, and ^3H -glucose specific activity will be measured. Indirect calorimetry to measure energy expenditure and substrate oxidation rates will be performed between 60-90 minutes.

Measurement of Hepatic Glucose Production With Drug Administration (HGP – Long): On the day of starting the treatment, the rate of endogenous (hepatic) glucose production will be measured with ^3H -glucose as described above with one difference. The ^3H -glucose infusion will be continued for 7 hours (8 in T2DM patients). After 2 hours of tracer equilibration (3 hours in T2DM patients), blood samples will be drawn from the catheter on the dorsum of the hand at -30, -20, -15, -10, -5 and 0 (time zero is drug ingestion time) minutes. At time zero, subjects will receive the first dose of the drug (placebo or empagliflozin 25 mg) and blood samples will be obtained from the retrogradely-placed catheter on the dorsum of the hand every 20-30 minutes for 5 hours. Plasma glucose, insulin, C-peptide, glucagon, GLP-1, cortisol, growth hormone, ketone, lactate, bicarbonate, and catecholamine concentrations, and ^3H -glucose specific activity will be measured. Urine will be collected during the equilibration period and after drug administration. Urinary volume and glucose concentration will be measured and urinary glucose excretion rate will be calculated. Indirect calorimetry to measure energy expenditure and glucose and fat oxidation will be performed 3 times through the study, from -60 to -30, from 150 to 180 and from 270 to 300 minutes. Blood will also be drawn to monitor renal function, electrolytes, glucosuria, and monitor and mitigate urinary tract infections.

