Norepinephrine turnover rate: The rate of total body norepinephrine spillover (release), which reflects total body sympathetic nervous system activity, will be measured with ^3H -norepinephrine (^3H -NE) infusion. Subjects will report to the CRC at 7 AM after a 10 hour overnight fast, and a catheter will be placed into an antecubital vein for tracer (^3H -NE) infusion. A second catheter will be placed retrogradely into a vein on the dorsum of the hand, which is placed in a heated box (60°C) for sampling of arterialized blood. The arterialized blood will be ascertained by measuring O_2 saturation (>95%). After drawing 3 baseline blood samples, a prime (3.6 μCi) -continuous (0.36 μCi) infusion of ^3H -NE will be started and continued for 2 hours. 4-6 arterialized blood samples will be drawn from the catheter on the dorsum of the hand at every 10-30 minutes. Plasma NE and 3,4-dihydroxyphenylglycol (DHPG) concentrations and ^3H -NE and ^3H -DHPG radioactivity will be measured. Previous studies (47,48) have demonstrated that this ^3H -NE infusion rate produces a steady state of plasma ^3H -NE radioactivity within 12 minutes without significant increase (<3%) in plasma ^3H -DHPG (the primary intraneuronal metabolite of norepinephrine) radioactivity. Blood will also be drawn to monitor renal function, electrolytes, glucosuria, and monitor and mitigate urinary tract infections.

Heart Rate Variability: Heart rate variability (HRV) will be measured in the morning after a 10-12 hour overnight fast. The measurement will be performed using the SphygmoCor device (AtCor Medical, Sydney, Australia) with the participant lying in the resting supine position for 10 min. This device takes into account only the normal heart beats, ignoring ectopic beats, and derives the time (SDNN and rMSSD) and frequency (LF and HF) domain parameters of the normal R-R intervals of the electrocardiogram (49). Parasympathetic nervous system (primarily represented by decreased high frequency domain [0.15-0.4 Hz] and rMSSD), and sympathetic nervous (primarily represented by decreased low frequency domain [0.04-0.15] and SDNN) system activity will be assessed before and at day 2 and week 12 of treatment with empagliflozin. Blood will also be drawn to monitor renal function, electrolytes, glucosuria, and monitor and mitigate urinary tract infections.

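### The 2-hour glucose that decides non-diabetic eligibility comes from an OGTT placed in random order among the baseline tracer studies, so tracer can be given before the criterion is checked

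*Combined protocol and SAP*

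**What the plan says.** **Eligibility.** Item 5 gives the first inclusion criterion for the main study's non-diabetic population as "FPG<126 and 2-h PG <200 mg/dl". Both parts are required.

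**Screening.** Under Specific Methods in Item 6, screening consists of a history, a physical examination, an EKG and blood tests: "Blood samples will be drawn for CBC, blood chemistries, lipid profile, thyroid function and HbA1c". No OGTT is listed. HbA1c is drawn, but Item 5 sets no HbA1c limit.

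**Baseline tests.** Study Design in Item 6 says "After screening, subjects will receive the following tests" and then lists five: HGP with substrate oxidation and hormones, ³H-NE turnover, heart rate variability (HRV), liver fat by MRS, and a 75-g OGTT. The schedule table also places the first OGTT at baseline. On sequence, the section says "The studies will be performed in a random order".

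**Timing within tests.** In the short HGP study the ³H-glucose infusion "will be started and continued for 3 (4 in T2DM patients) hours", and sampling starts "After 2 hours (3 hours in T2DM patients) of tracer equilibration". The ³H-NE infusion "will be started and continued for 2 hours", with no difference between groups.

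**Randomization.** The 2:1 allocation to empagliflozin or placebo takes place once all the baseline tests are complete.

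**The concern.** An inclusion criterion is normally settled before research procedures begin. Here the value it needs is produced by one of those procedures, at a point left to a random sequence. Someone who passes on fasting glucose can therefore have one or both tritiated infusions before anyone knows whether the 2-hour criterion is met.

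The HGP study adds a second difficulty. Its infusion length, equilibration time and sampling window depend on whether the person is treated as diabetic, so the group must be decided before the test is run. If the 2-hour value later comes back at 200 mg/dl or more, the HGP data already collected follow the non-diabetic schedule. The plan does not say what is then done with the person or with the data.

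**Working it through.** **1. The plan's own figures.** The plan gives no number on this point. The nearest is the main-study Sample Size Calculation, which supplies the group size used in step 4. Reading the ± as an SD and alpha as two-sided, 0.34 / [0.26 × √(1/10 + 1/20)] = 3.376. Subtracting 1.960 leaves 1.416, which is power of 92.2% (90.3% by noncentral t) against a stated figure above 90%. Allowing for one sixth dropping out, 30 / (1 − 1/6) = 36. Both figures reproduce, and nothing below changes them.

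**2. Where a 2-hour glucose could come from before the tracer studies.**

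| Place in the plan | Gives a 2-hour glucose? |
|---|---|
| Item 5, non-diabetic row | Requires it, names no source |
| Item 6, Screening | No |
| Item 6, baseline tests | Yes: the OGTT, in random order with the other four |
| Schedule table | OGTT at baseline and 12 weeks only |

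No other section supplies an earlier value.

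**3. Chance that tracer comes first.** Assume every order of the five tests is equally likely and the tests fall on separate occasions. Only the relative order of OGTT, HGP and NE matters, which leaves 3! = 6 orders.

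- OGTT before both tracer studies: 2/6 = 1/3.
- At least one tracer study before the OGTT: 1 − 1/3 = 2/3 (80 of the 120 full orders).
- Both tracer studies before the OGTT: 2/6 = 1/3.
- HGP before the OGTT: 1/2.
- OGTT first of all five tests: 1/5.

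The 2/3 applies to tracer exposure. The 1/2 applies to the group-specific timing, because only HGP has it.

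**4. Expected number of people.** The documents do not say what share of people with fasting glucose below 126 mg/dl have a 2-hour value of 200 mg/dl or more, so I assume 3–10%. The Sample Size Calculation sets 36 per group. The Data Analysis Plan names normal glucose tolerance (NGT), impaired fasting glucose (IFG) and T2DM as groups, which gives 2 × 36 = 72 non-diabetic entrants. Item 5 lists only one non-diabetic population in the main study, so 36 is shown as well.

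| Entrants | Assumed share | 2-h PG ≥200 | Any tracer first (× 2/3) | HGP first (× 1/2) |
|---|---|---|---|---|
| 72 | 3% | 2.16 | 1.44 | 1.08 |
| 72 | 10% | 7.2 | 4.8 | 3.6 |
| 36 | 3% | 1.08 | 0.72 | 0.54 |
| 36 | 10% | 3.6 | 2.4 | 1.8 |

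With the OGTT done before any tracer study, the last two columns become zero.

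**The case against.** The strongest reply is that the 2-hour value exists before anything irreversible happens. Randomization waits for all the baseline tests, the OGTT included, so the result is available before allocation and before the first dose. This stands. A reader might infer that people with diabetes will enter the non-diabetic group and compromise the NGT and IFG inference, but that would require the result to be ignored. The plan does not say how the result is acted on, but it does make the value an inclusion criterion, and nothing in it implies that the criterion would be waived.

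Four further limits also stand:

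- **Not both studies on the wrong schedule.** The ³H-NE study is the same in every group, so the 2/3 must not be attached to mistimed data.
- **Not necessarily barred from the trial.** The main-study T2DM row asks for fasting glucose below 240 mg/dl with no lower bound. A person with fasting glucose under 126 and a raised 2-hour value might enter that group, with NE, HRV and MRS data still usable.
- **HGP data not shown to be unusable.** The documents do not say why T2DM subjects get the extra hour, and the tracer prime is scaled to fasting glucose. The data would be off the T2DM schedule; more than that is inference.
- **The radiation dose is probably modest.** Sub-Study 2 quotes 13.4 mrem for a 10-hour ³H-glucose study. The non-diabetic baseline infusion lasts 3 hours with the same prime formula, so its dose should be lower. No figure is given for ³H-NE.

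Finally, the phrase on random order may mean only that no order is fixed. The 2/3 and 1/2 would then depend on each site's habits. The text would still allow tracer before the eligibility result.

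**Conclusion.** The point holds as a sequencing fault in the main study: a required inclusion value is obtained after screening, at an unfixed place among the tracer studies. With a uniform order, 2/3 of people entering baseline testing as non-diabetic would have some tracer study before the OGTT, and 1/2 would have HGP before it. These are shares of entrants, not of everyone screened, since screen failures get no tracer. Most of these entrants are eligible and would be infused anyway.

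Those affected are the few whose 2-hour value proves to be 200 mg/dl or more: about 1–5 with any tracer first and about 1–4 with HGP first, on an assumed 3–10% of 72 entrants, and about half that if only 36 non-diabetic entrants are meant. Their loss is avoidable baseline tracer exposure and an HGP study on a schedule chosen before their group was known. Study drug exposure, sample size, power and the planned analysis are not touched. The correction is worth making because it costs so little. The Sub-Study non-diabetic row uses fasting glucose alone, so the point does not extend to it.

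**What to change.** In Item 6, make the existing baseline OGTT the last step of screening, ahead of any tracer study. State that the 2-hour criterion and the assignment to group are settled on that result, including how a value of 200 mg/dl or more is handled. Limit the random order to HGP, NE turnover, HRV and MRS, and update the schedule table to match. The same OGTT serves as the baseline measurement, so no test is added.

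The change takes about one sentence in each of Study Design and Screening. A few OGTTs will be done in people who are then excluded; placing the test last in screening keeps that number down. The baseline OGTT will also always come before the other tests, so its position no longer varies between people.
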